## **1. LAY DESCRIPTION**

It is well documented that Stroke survivors need to perform hundreds of repetitions in rehabilitation to regain functional recovery. In this study we want to establish the most effective instructions for increasing repetitions.

## **2. BACKGROUND**

To optimise outcomes after Stroke large amounts of practice are required (1). In fact, hundreds of repetitions per day may be essential for neural changes to occur (2). However, patients in rehabilitation units spend the majority of their day inactive and only a small part of their day engaged in active practice (3). Even during therapy sessions patients may achieve very few practice repetitions (4).

Therapy intensity may be increased through the delivery of instructions for example, Stroke survivors respond to instructions that encourage speed (5, 6), thus they may have the capacity to do more repetitions in a certain time period. Additionally, instructions that focus on the external environment require less cognitive demand than those that focus on body movements, and result in more repetitions being performed (7-9).

However, there is very limited research on the way that instructions impact the number of repetitions that are performed by Stroke survivors in rehabilitation. This research will examine the types of instructions that result in the fastest rate of

repetitions. This will be helpful to inform therapists of the best instruction to use to increase the intensity of practice during Stroke rehabilitation.

### **3. AIM / OBJECTIVES**

The broad aim of this study is to determine strategies to increase the number of repetitions performed during therapy sessions. This study aims to quantify the effect of different types of instructions on the amount of time it takes to complete a set of repetitions.

The research question is:

What are the most effective instructions to increase repetitions performed by Stroke survivors in rehabilitation?

## **5. RESEARCH PLAN / STUDY DESIGN**

### *Type of study:*

This will be a randomized cross-over study.

### *Data collection:*

The Stroke survivor will do their usual exercises in Bankstown-Lidcombe rehabilitation gym. The researcher will observe the participant perform twenty five repetitions of one exercise under no instruction. This will be timed to form a baseline. Following this, the researcher will use one of three different types of instructions to direct their practice of the same exercise. The participant will receive a different instruction each day across three days. The order of these three types of instructions will be randomised giving six possible orders. Each patient will be randomly assigned to one of the six orders..

The types of instructions that will be used will be (using standing up as an example); an instruction with an endpoint such as “can you stand up and sit down 25 times”, an instruction with a time component such as “can you stand up and sit down 25 times as fast as you can”, and an instruction with motivation such as “can you stand up and sit down 25 times as fast as you can, aim for your personal best!!”.

The order of the instructions will be randomised across the three days allowing for each of the three instructions to be used. The time taken to perform the twenty five repetitions under each instruction will be recorded.

A new baseline will be measured each day to account for recovery over the three days. Data will be collected at a similar time each day to reduce the risk of fatigue affecting rate of repetitions.

*Source of participants:*

The participants for this study will be Stroke survivors admitted to Bankstown Stroke unit who meet the inclusion criteria.

*Sample size*

There are three different instructions that are being tested. The order of instructions will be randomized. There are six different orders that the instruction can be presented. Therefore, the participants will be randomised to one of six groups. Six groups of three participants will be recruited to account for any affect that the order of instructions has on the rate that the repetitions are performed. Therefore, a total of approximately eighteen participants will be recruited for this study.

*Inclusion criteria:*

- Stroke is diagnosed by clinical presentation, CT or MRI scan results
- All Stroke types are eligible (haemorrhagic or ischaemic)
- The admission period is likely to be more than one week
- The participant can perform 50 repetitions of either stand ups, tilt table or sit and reach without physical assistance

*Exclusion criteria:*

- The patients do not require physiotherapy intervention during their admission
- Not medically stable to perform exercise
- Are unable to follow one-stage commands
- English is not sufficient to understand instructions

*Justify exclusion criteria:*

Stroke patients who are not requiring physiotherapy intervention in the form of repetitive exercise are not included as this is required for intensity of practice to be measured.

If the patient is not medically stable, performing exercise may be of risk to the participant.

The participant must be able to follow one-stage commands to understand the instruction that is being delivered to them and for different instructions to have an affect of the rate of repetitions.

The participant must have English competency to the level of understanding the instructions delivered to them. This enables them to respond to the different instructions, resulting in a different rate of repetitions for each.

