### *Data analysis*

For each instruction, the recorded time for twenty five repetitions will be converted to a rate of repetitions/minute. The time taken to perform the twenty five repetitions under instruction will be compared with baseline to calculate an percentage increase in rate of repetitions.

A repeated measures ANOVA will be used to ascertain the effect of the different types of instructions on the percentage increase in rate of repetitions.

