The risks in this intervention are no greater than the usual demands of exercise. To manage the risks of exercise, there will always be one researcher and one other physiotherapist present when the participants are performing their exercise. They will be closely observed to ensure they are not experiencing discomfort whilst exercising. The participant will also be informed that they should stop exercising if they experience pain, or discomfort.

Furthermore, participants will be excluded from the study if they are medically unstable, as determined by the medical team.

The instructions delivered to the participants are not different to what would commonly be used in clinical practice. Therefore, the participants are very unlikely to exert themselves beyond what they would in normal rehabilitation.

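### Nothing keeps the day's instruction from whoever runs and times the baseline, which is the reference for that instruction's result; opening it only after the baseline is a cheap partial safeguard

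*Protocol*

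**What the plan says.** Protocol section 5, Data collection, sets the sequence for each day. First, "The researcher will observe the participant perform twenty five repetitions of one exercise under no instruction", and "This will be timed to form a baseline". Then, "Following this, the researcher will use one of three different types of instructions to direct their practice of the same exercise". The instructions follow a pre-assigned order: "Each patient will be randomly assigned to one of the six orders", and "The participant will receive a different instruction each day across three days". The baseline is repeated daily: "A new baseline will be measured each day to account for recovery over the three days".

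Section 5, Data analysis, converts times to rates. The instructed set is "compared with baseline to calculate an percentage increase in rate of repetitions", and that percentage goes into a repeated measures ANOVA across the three instructions.

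Section 6, Risks, states that "there will always be one researcher and one other physiotherapist present when the participants are performing their exercise". The second person is there for safety and is given no measurement task.

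The text available for review does not say who prepares or holds the order, when the day's instruction becomes known to the researcher, or who holds the stopwatch for either set.

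**The concern.** The outcome is a ratio, and its reference value is measured afresh before each instruction. If the person conducting the uninstructed set already knows that a speed or motivation instruction comes next, the set may be run or timed a little differently from the one before a plain endpoint instruction. Pace, tone and casual encouragement are the likeliest routes, because the uninstructed condition has no script.

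A slower baseline before one instruction raises that instruction's percentage increase, and a faster one lowers it. The error follows the instruction and not the day. It therefore recurs in all six orders and does not average out. Having each participant serve as their own control does not help either, because the error varies within the participant.

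The instructed set cannot be masked from the person who gives the instruction. The baseline is the one measurement that can be at least partly masked, because nothing has been said yet.

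**Working it through.** **Inputs from the protocol.** Three instructions, one per day without repeats; six orders; three participants per order; a new baseline each day; outcome defined as the percentage increase in rate over baseline. **Assumed, not in the protocol:** the size of any baseline error and the true gain.

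**The plan's own figure.** 3! = 6 orders, and 6 × 3 = 18 participants, as stated. That gives 18 × 3 = 54 baselines, 18 on each day.

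**Sensitivity of the outcome.** Both sets have 25 repetitions, so the outcome is 100 × (T_baseline / T_instructed − 1). If the baseline time is overstated by a fraction b and the true gain is g, the observed gain is (1 + b)(1 + g) − 1. The shift is b(1 + g).

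| Assumed b | Shift at g = 0% | at g = 20% | at g = 30% |
|---|---|---|---|
| 2% | 2.0 points | 2.4 | 2.6 |
| 5% | 5.0 points | 6.0 | 6.5 |
| 10% | 10.0 points | 12.0 | 13.0 |

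In seconds, with invented times: 100/90 − 1 = 11.1% and 105/90 − 1 = 16.7%, a difference of 5.6 points.

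What matters is an error that differs by instruction. An error common to all days mostly cancels: with b = 5% everywhere and true gains of 0% and 20%, the contrast moves by only 0.05 × (0.20 − 0) = 1.0 point.

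**How far late disclosure masks the baseline.** Suppose the researcher who gave the earlier instructions learns each day's instruction only after the baseline. The chance of naming it beforehand is 1/3 on day 1, 1/2 on day 2 and 1 on day 3, with mean (1/3 + 1/2 + 1)/3 = 0.61. Without concealment it can be 1 on every day. The 18 day-3 baselines, of 54, stay unmasked.

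**Effect on the bias in a simple model.** Let the baseline error be b times the believed probability that a favoured instruction comes next, averaged over the six orders.

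- Order known throughout: favoured instruction 1.00b, each other 0. Contrast 1.00b.
- Disclosure after the baseline: favoured 1/9 + 1/6 + 1/3 = 0.611b; each other 1/9 + 1/12 + 0 = 0.194b. Contrast 0.42b.
- The same, with day 3 handled by someone unaware of days 1 and 2: favoured 1/9 + 1/6 + 1/9 = 0.389b; each other 1/9 + 1/12 + 1/9 = 0.306b. Contrast about 0.08b.

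The model shows direction and relative size only. It does not show that b is other than zero.

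**The case against.** The strongest reply is that the protocol is silent here and not wrong. Both timings are in the passive, no timer is named, and nothing says the researcher sees the order before the baseline. Some pages were not available for review, so a statement on roles elsewhere cannot be excluded. This stands to the extent that foreknowledge is possible and not established. A reader might infer that the same researcher times both sets while knowing what comes next; the protocol does not say so. It does, however, fix that the same role observes the baseline and then gives the instruction, with the whole order already assigned.

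A second reply is that timing 25 counted repetitions leaves little discretion, and that an observed, uninstructed set of usual exercises already limits interference. This largely holds for the stopwatch. It holds less well for the participant's pace, which an observer can influence without meaning to.

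Third, a reader might infer that the baseline can be fully masked with the staff already present. The documents do not support that. The second physiotherapist attends whenever participants exercise. If it is the same person each day, they have heard the first two instructions and can deduce the third. Changing only who holds the stopwatch also leaves an informed researcher running the set.

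Fourth, the instructed set stays exposed. A 5% error there, 90 s to 85.5 s against a 100 s baseline, moves 11.1% to 100/85.5 − 1 = 17.0%, as large an effect as on the baseline. This is correct: masking the baseline protects one half of the ratio only.

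**Conclusion.** The concern holds in a limited form. The protocol does not keep the day's instruction from whoever conducts and times the baseline, and that baseline is the reference for the only outcome analysed. For a true gain of zero or more, a baseline error that differs by instruction enters the contrast at least one-for-one, and the cross-over does not cancel it.

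The size is unknown. The table in the working rests on assumed errors of 2% to 10%, and it would be a misreading to take 5 or 6 points as the expected bias. Disclosing the instruction after the baseline reduces the exposure, from 1.00b to 0.42b in the simple model, but does not remove it. The point deserves action because the safeguard is nearly free, not because bias has been shown. It concerns the conduct of the sessions, so it belongs in the protocol and cannot be repaired at analysis.

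**What to change.** In section 5, Data collection, add that each participant's instructions are kept in sealed, day-numbered envelopes prepared by someone who does not run the sessions, and that each envelope is opened only after that day's baseline time has been written down. Name who runs and who times each set.

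State the limit openly: day 1 is fully masked, day 2 partly, and day 3 not at all for anyone present on the earlier days. Where rostering already allows, have the day-3 baseline both run and timed by a physiotherapist who did not attend that participant's earlier sessions. Otherwise, report the day-3 baselines as unmasked.

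The cost is envelope preparation and a few sentences of procedure. Masking remains incomplete. If the physiotherapist present for safety takes on the day-3 timing, the text must also show how that fits with the close observation described in section 6, Risks. The sample size and the planned analysis are unchanged.

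### A set stopped for pain or discomfort has no outcome value, and a classical repeated measures ANOVA would then normally lose that participant's other days too

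*Protocol*

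**What the plan says.** Protocol section 5, Data collection, fixes a baseline set and an instructed set of 25 repetitions on each of three days: "The participant will receive a different instruction each day across three days". For the instructed sets, "The time taken to perform the twenty five repetitions under each instruction will be recorded"; the baseline set is timed in the same way, and a new baseline is taken each day.

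Under Data analysis, "the recorded time for twenty five repetitions will be converted to a rate of repetitions/minute", and the instructed set "will be compared with baseline to calculate an percentage increase in rate of repetitions". The method is then named: "A repeated measures ANOVA will be used to ascertain the effect of the different types of instructions" on that percentage.

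Protocol section 6, under Risks, adds: "The participant will also be informed that they should stop exercising if they experience pain, or discomfort". The same section says that "the participants are very unlikely to exert themselves beyond what they would in normal rehabilitation". The inclusion criteria in section 5 require that "The participant can perform 50 repetitions of either stand ups, tilt table or sit and reach without physical assistance".

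The protocol gives no partial-set rate, repeat, replacement or other value for a set that is stopped. It does not say what the ANOVA does with an incomplete participant, and it gives no expected frequency of stopping.

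**The concern.** The protocol foresees that a set may be stopped, but its outcome exists only for a set that is finished. The percentage change needs both of the day's times, so a stop in either set leaves the day empty.

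The gap matters for the question asked. The trial wants to know which instruction yields more repetitions. If an instruction makes someone stop early, that is evidence about the instruction, yet the outcome as defined records nothing.

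The named analysis can enlarge the loss. A classical repeated measures ANOVA uses only people with all three conditions, so one empty day would normally discard two valid ones and leave fewer than three people in that order group. Three per order is the only stated basis for the sample size.

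The raw information may also be lost for good. Section 6 has the paper records shredded after transfer to the spreadsheet. If repetitions completed and elapsed time are not noted during the session, no later analysis plan can rebuild them.

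**Working it through.** **The plan's own figure.** Six orders × 3 participants = 18, which matches the stated total of approximately eighteen. No power, effect size, standard deviation or allowance for loss is given, so nothing further can be reproduced.

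**Load against eligibility.** One day asks for 25 baseline + 25 instructed = 50 repetitions, which is exactly the entry criterion. The criterion sets no speed, whereas two of the three instructions ask for maximal speed.

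**Complete participants.** Let p be the probability that a fast set is stopped. Assume the same p, independently, in each of the two fast sets, and no stops in the baseline or endpoint sets. The documents give no value for p, so a range is shown.

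- Probability that a participant is complete: c = (1 − p)²
- Expected complete participants: 18c
- Chance of losing at least one: 1 − c¹⁸
- Valid instructed sets discarded under complete-case analysis, of 54: 18 × [3(1 − c) − 2p]

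| Assumed p | c | Complete of 18 | Chance of losing at least one | Valid sets discarded |
|---|---|---|---|---|
| 2% | 0.960 | 17.3 | 52% | 1.4 |
| 5% | 0.902 | 16.2 | 84% | 3.5 |
| 10% | 0.810 | 14.6 | 98% | 6.7 |
| 15% | 0.722 | 13.0 | 99.7% | 9.6 |

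Example at 5%: 18 × 0.95² = 16.2.

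**Precision.** The smallest detectable paired difference, in standard deviations of the difference, was taken from the noncentral t distribution (assumed 80% power, two-sided 0.05). It is 0.70 at n = 18, 0.75 at 16, 0.78 at 15 and 0.85 at 13.

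**Direction of bias.** This was simulated with 20,000 trials of 18. Assumed mean gains were 5% (endpoint), 20% (speed) and 25% (motivation), so the true contrast of fast against endpoint is (20 + 25)/2 − 5 = 17.5 points. The assumed between-person standard deviation of response to the fast instructions was 15 and the residual standard deviation 8. Stopping followed a logistic model in the person's response. The mean contrast among complete participants was:

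| Who stops | p = 2% | 5% | 10% | 15% |
|---|---|---|---|---|
| Weak responders | 18.3 | 19.3 | 20.6 | 21.9 |
| Unrelated to response | 17.5 | 17.5 | 17.5 | 17.5 |
| Those who push hardest | 16.7 | 15.8 | 14.3 | 13.0 |

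At the same stop rate the contrast is inflated, unchanged or reduced according to who stops.

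**The case against.** The protocol does not say that incomplete participants are dropped. It only names a repeated measures ANOVA, and the handling of incomplete data, missed days and early discharge is commonly left to an analysis plan, which may exist here. This stands: deletion is the usual behaviour of the classical method, not protocol text. It does not answer the gap in data capture, because an analysis plan cannot use numbers that nobody recorded.

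Stopping may be rare. Participants must be able to do a full day's repetitions, medically unstable patients are excluded, and the protocol expects no exertion beyond normal rehabilitation. This stands as a reason to expect low rates. At an assumed 2% per fast set the loss is under one participant on average (18 − 17.3 = 0.7). None of this text rules out stopping at maximal speed.

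A participant who stops may rest and then finish, so a stop need not mean a missing time. The protocol does not settle whether the set continues or how the pause is timed. That is the same gap seen from another side.

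A reader might infer that the fast instructions will look better than they are, because those who tolerate them worst are removed. The documents do not support that. Stops can also occur in baseline or endpoint sets, and those who stop may be the ones who pushed hardest, which reverses the bias. Nor does comparing finishers with everyone under a single instruction show the bias: complete-case deletion changes all three means, and the relevant quantity is the within-person contrast.

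The remedy has limits too. A rate from a shortened set reflects a less tired participant, and a mixed model does not cure missingness that depends on the unobserved response.

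**Conclusion.** The point holds in a limited form. A set stopped under the protocol's own instruction has no defined outcome, in a trial of about 18 people, and the classical form of the named method would normally lose the participant's valid days as well.

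Under the assumed rates of 2%, 5% and 10% per fast set, 17.3, 16.2 and 14.6 participants remain complete. The loss of precision is small at the low end (0.70 to 0.75 standard deviations if two people are lost) and larger if five are lost (0.85). Bias in either direction is possible, and so is none. In the illustration, a true contrast of 17.5 points is estimated anywhere from 14.3 to 20.6 at 10% stopping.

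All stop rates, gains and standard deviations are assumptions. The protocol establishes neither that the ANOVA will delete participants, nor that stopping will differ by instruction, nor the sign of any bias. The change should be made because it is cheap and works only if it is in place when the data are collected.

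**What to change.** Leave the stop instruction as it is and change what is recorded and how it is analysed.

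1. For every set, including baseline, record the repetitions completed and the elapsed time. The outcome is already a rate, so a stopped set gets repetitions completed divided by elapsed minutes. State how a paused and resumed set is timed.
2. Analyse all available days in a linear mixed model, with instruction and day as fixed effects and participant as a random effect.
3. Report the number of stopped sets by instruction, with baseline sets shown separately.
4. Add a sensitivity analysis that gives stopped sets the lowest observed rate change. It is needed because a shortened set may overstate the rate, and because the mixed model assumes that any day still without a value is missing at random.

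The cost is one extra field on the data sheet and slightly more analysis work. The remaining weakness is that a shortened instructed set may flatter the instruction, while a shortened baseline may do the opposite by raising the comparator. The counts of stopped sets let a reader judge how much this matters.

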### *Recruitment of participants*

During the period of data collection, [name] will meet with all potential participants who meet the inclusion criteria. She will present them with participant information and consent form and return in two days, allowing them time to read over the information presented to them and discuss it with family.

